4.3.2 Use in Female Subjects of Childbearing Potential

Female subjects of childbearing potential must consent (without any element of coercion) to use a double-barrier method for birth control (e.g. condoms with spermicide) if sexually active. A pregnancy test will be performed at the Screening Visit.

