Study Population: Subjects eligible for study participation will be healthy by Structured Clinical Interview for Diagnostic Statistical Manual-IV (SCID) criteria. Subjects will be between 18-70 years of age (have not had 71st birthday) on the date of screening. Subjects who will be permitted into the study include those who meet all the inclusion criteria and have none of the exclusion criteria.

Duration of Participation:	Subjects will be followed in the study for 5 weeks.
Endpoints:	
Engagement of cerebral blood flow – The effect of TLT on cognition will be assessed before and after each session (c-TLT, s-TLT and p-TLT) by measuring the Diffuse Correlation Spectroscopy (DCS) signal.
 
Engagement of cerebral electrical activity – The effect of TLT on brain electrical waves will be assessed before and after each session (c-TLT, s-TLT and p-TLT) by measuring the Electro-Encephalographic (EEG) signal.
 
Engagement of cognitive circuitry – The effect of TLT on working memory will be assessed immediately after each session by n-back task.
 
Safety - The safety endpoints will evaluate any reported adverse events within one week from each sessions of TLT.

Entry Criteria: Inclusion Criteria	
	
 1. Subject's age at screening will be between 18 and 70 years old (inclusive). 2. Women of child-bearing potential must use a double-barrier method for birth control (e.g. condoms plus spermicide) if sexually active. 3. Subject Informed Consent obtained in writing in compliance with local regulations prior to enrollment into this study. 4. The subject is willing to participate in this study for at least 5 weeks.
Exclusion Criteria:	
	
 1. The subject is pregnant or lactating. 2. The subject is on any psychotropic medication. 3. Psychotherapy is exclusionary unless the subject has had at least 8 weeks of treatment prior to the screening visit. 4. Any current psychiatric disorder (per SCID assessment) 5. Substance or alcohol dependence or abuse in the past 6 months. 6. History of a psychotic disorder or psychotic episode (current psychotic episode per SCID assessment). 7. Bipolar affective disorder (per SCID assessment). 8. Unstable medical or neurological illness, defined as any illness which is not well-controlled with standard-of-care medications (e.g., insulin for diabetes mellitus, HCTZ for hypertension). 9. Suicidal or homicidal ideation as determined by SCID screening.

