ELATED-2 was a double-blind, randomized, controlled study of 8 weeks of TLT (Omnilux New U - LED, 830 nm; 36.2 mW/cm²; up to 65.2 J/cm²; vs. sham for 16 sessions). At endpoint, the mean HAMD-17 for depression decreased of 11.7±7.5 points (TLT, n=9) vs. 5.3±7.0 points (sham, n=9) (p=0.04); the differences were even more pronounced in the completers sample as HAMD-17 decreased of 15.7±4.4 (TLT, n=6) points vs. 6.1±7.9 points (sham, n=7) (p=0.01).

These findings suggest that TLT could be a novel intervention for subjects with MDD. Both the Laser study (ELATED-1) and the LED study (ELATED-2) were conducted by our group at Massachusetts General Hospital (MGH).

NIR-flow (the present submission) will test for the first time the biological underpinning of TLT, by focusing on the effect of TLT on cerebral blood flow.

The LiteCure® The PhotoBioModulation-1000 (TPBM-1000) device to be used in this study does not require Food and Drug Administration (FDA) approval. In fact, the TPBM-1000 device used in this study is considered a non-significant risk device because:

- TPBM-1000 dose does not exceed the Maximum Permissible Exposure (MPE) for skin – Center for Devices and Radiological Health (CDRH), 21CFR1040.10 and 21CFR1040.11;
- TPBM-1000 is substantially equivalent to the OmniLux New U device (used in ELATED-2 at MGH), which the FDA has already categorized as a non-significant risk device;
- TPBM-1000 differs from the OmniLux New U only in that it provides an additional site of irradiation – treatment is delivered to EEG sites FP1 and FP2 in addition to F3 and F4 on the forehead;
- currently FDA-cleared LED devices are typically available over-the-counter and are considered safe to use without professional supervision.

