4.2 Study Design

This study is a single-blind, sham-controlled, study on the use of Transcranial continuous light therapy (c-TLT) and pulse light therapy (p-TLT) as an enhancer of cerebral blood flow in healthy subjects.

We expect that out of 30 subjects enrolled 10 subjects will be eligible to complete a sequence of three sessions of Transcranial Light Treatment (TLT) and sham.

All eligible subjects will receive two TLT sessions and one of sham (s-TLT) within the course of 5 weeks. While the sequence (c-TLT, s-TLT, p-TLT) will be the same for all subjects, the subjects will be blind to the specific mode of function used in each session.

The study site (MGH) will have one Litecure device, which will recognize the subjects' codes generated by the study statistician. Only subjects will be blind to the treatment group assignment. The Sham treatment consists of applying all the procedures for the delivery of the TLT, while actually delivering no light. The blinding of the sham will be effective because the radiation is not visible and because the active therapy (continuous or pulsed) will not produce any subject-discriminable difference from sham, e.g., skin warming. The sham treatment will mimic the TLT procedure. The treatment will be bilateral and applied to the frontal areas with two application sites on the left side and two on the right side [left and right forehead centered on EEG sites on F3, F4, Fp1, Fp2]. Energy is administered with a radiation wavelength of 830 nm. The duration of irradiation is 20 minutes at each application site (the 4 sites are irradiated at the same time which is equivalent to 20 minutes of total time). The entire sessions is estimated to last about 1.5 hours. The additional time is needed to have the subject complete a urine toxicology and self-report forms, to prepare the subject, to place the necessary protections (e.g. goggles), to inspect the subject's skin, to complete DCS before and after TLT, to set the TLT devices, and to give the subject time to rest after the irradiation. TLT treatment will only be administered by licensed physicians (i.e. MDs) who are on study staff. All staff who deliver treatment must pass training that is approved by the MGH Laser Safety Committee. The treatment will follow these specifications: wavelength 830 nm; average irradiance 54.8 mW/cm²; average fluence of 65.8 J/cm² (consistently with energy density used in the ELATED-2 study at MGH with the device Omnilux New U).

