4.8 Detailed Study Visits

4.8.1 Screening Visit – Visits 1 (Week 1)

Purpose

The purpose of the Screening Visit will be to determine the eligibility of subjects for participation in the NIR-flow study.

Procedures

The screening visit will occur at the MGH Center for Anxiety and Traumatic Stress Disorders (CATSD) in Boston. At this visit subjects will be consented for the study, will receive a psychiatric evaluation, and will be screened for presence of psychiatric disorders using the Structured Clinical Interview for Diagnostic Statistical Manual-IV (SCID-IV). The SDQ, ASQ and PANAS will be used to assess for subthreshold symptoms. The SFI and NEURO-QoL will be used to assess sexual and cognitive functioning.

Routine laboratory tests (Urine Tox Screen and Urine Pregnancy Test) and complete physical exam including vitals and weight will be performed at screen; the tests will be processed by a laboratory at MGH.

Once all tests and procedures become available for review, the Investigator will then proceed to closely re-evaluate the subject for all the inclusion and exclusion criteria.

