4.8.2 TLT-DCS Visits – Visits 2-4 (Weeks 2-4)

The TLT sessions will occur once weekly for three weeks at the MGH Martinos Center for Biomedical Imaging in Charlestown. Subjects missing one session will be allowed to still receive their TLT session, by shifting the overall study schedule of one week. The study PI will be an active participant in the delivery of the TLT. The PI and other collaborators from MGH CATSD will assist with the delivery of TLT. The device TPBM-1000 for the administration of the TLT will be provided by Litecure Inc. Litecure will provide training of MGH CATSD staff in the use of the device and will provide training certificates at the completion of the training.

The overall study visit is estimated to last about 1.5 hours. The TLT session is estimated to last about 50 min – 5 minutes of EEG before DCS, 10 minutes of DCS before TLT, 20 minutes of TLT, 10 minutes of DCS after TLT and 5 minutes of EEG after DCS. EEG recording will extend to cover at least part of the time devoted to the cognitive tasks. Study sessions will take place in an office dedicated to TLT treatment at MGH Martinos Center for Biomedical Imaging in Charlestown. Only the subject and the staff administering the TLT will be allowed in during the session. The subject will comfortably lie down on an exam bed or sit on a recliner. The sites of application of TLT (left and right forehead) will be inspected for any possible skin lesions (e.g. laceration or signs of inflammation) which would contraindicate the treatment. The study staff administering the TPBM device at the TLT-DCS sessions will appropriately remove any reflective objects to fall into or obstruct the path of the light energy produced by this device. Both the subject receiving the TLT and the study staff will wear protective eyewear in the form of goggles. During treatment sessions the office will be kept completely dark and a warning sign will hang at the office door. The staff will be provided training on basic safety procedures relative to the use of the device.

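### Pregnancy is an exclusion but is tested only at Week 1 screening, so the two active light sessions rely on a result nominally 7 and 21 days old; a urine strip on the day would be a cheap, minor safety improvement.

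*Combined protocol and SAP*

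**What the plan says.** The first exclusion criterion in the Study Summary is "The subject is pregnant or lactating". Section 4.3.2 places the test at entry: "A pregnancy test will be performed at the Screening Visit". Section 4.8.1 confirms that it is a urine test: "Routine laboratory tests (Urine Tox Screen and Urine Pregnancy Test) and complete physical exam including vitals and weight will be performed at screen".

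Section 4.8.2 lists the tasks done before every light session. Urine toxicology is repeated there; a pregnancy test is not. I rely on this list rather than on the attached time table, whose text as extracted shows no pregnancy test even at screening.

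The order is fixed: continuous light at Visit 2, sham at Visit 3, pulsed light at Visit 4. Section 4.2 describes the sham: "The Sham treatment consists of applying all the procedures for the delivery of the TLT, while actually delivering no light". The spectroscopy probe emits a little near-infrared light at all three visits (3.3), but treatment light comes only at Visits 2 and 4.

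After screening, protection rests on contraception: "Women of child-bearing potential must use a double-barrier method for birth control", which applies if the subject is sexually active. Section 6.3 names contraception among the steps taken to reduce possible risks of the treatment, and adds that no teratogenic effect has been linked to it. Section 3.1 states that "the TPBM-1000 device used in this study is considered a non-significant risk device because", and gives the reasons.

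**The concern.** An exclusion protects a subject only while the evidence behind it is current. Here that evidence is collected once, one week before the first active session and three weeks before the second.

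The other safeguards do different work:

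- Contraception is agreed when the subject consents, which happens at the screening visit. It cannot prevent a pregnancy that already exists then but is too early to detect.
- The adverse-event and concomitant-medication forms, completed before each session, can bring a known pregnancy to light. They do not look for an unknown one.
- Section 4.19.1 lets the subject or the investigator end participation at any time. That permits action but gives nothing to act on.

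At stake is an avoidable light exposure in an undetected pregnancy. At most 10 subjects x 2 active sessions = 20 sessions are concerned, and fewer in practice, because both sexes and ages 18 to 70 are eligible.

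**Working it through.** The plan gives no figure on this point, so there is none to reproduce.

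**Age of the result.** Sections 4.7 and 4.8 put screening in Week 1 and Visits 2, 3 and 4 in Weeks 2, 3 and 4. Nominal age = (visit week - 1) x 7 days.

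- Visit 2: (2 - 1) x 7 = 7 days. Visit 4: (4 - 1) x 7 = 21 days.
- Section 4.8.2 lets the schedule move by one week after a missed session. Visit 4 then falls on day 28. Visit 2 falls on day 14 only if the shift comes before it.
- No window between screening and Visit 2 is stated. By week label alone the ages could run from 1 to 13 days at Visit 2 and from 15 to 27 at Visit 4.

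**What a retest could find.** Assumption, not in the documents: a urine test turns positive L = 14 days after conception (range 10 to 16). Screening is day 0, and screening misses conceptions from the L days before it. A retest on day d is positive for conceptions up to day d - L. Therefore:

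- pre-screening days missed at screening and found on day d: min(L, d) of L
- post-screening days found on day d: max(0, d - L) of d
- distinct days found by Visit 4: from -L to 21 - L, which is 21 days at any lag in the range

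| L | Visit 2, before screening | Visit 2, after screening | Visit 4, before screening | Visit 4, after screening | Share of the 21 distinct days before screening |
|---|---|---|---|---|---|
| 10 | 7/10 = 70% | 0/7 | 10/10 | 11/21 = 52% | 10/21 = 48% |
| 14 | 7/14 = 50% | 0/7 | 14/14 | 7/21 = 33% | 14/21 = 67% |
| 16 | 7/16 = 44% | 0/7 | 16/16 | 5/21 = 24% | 16/21 = 76% |

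**Which visit finds them.** With strips at Visits 2 and 4 only, 7 of the 21 days are first found at Visit 2 and the other 14 at Visit 4. With a strip at Visit 3 as well, first detections split 7, 7 and 7. Visit 3 averts no further active session, because the Visit 4 strip would find the same pregnancies, but it finds some a week earlier.

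**What remains.** At L = 14, conceptions from 21 - 7 = 14 of the 21 days after screening still cannot be detected at Visit 4. A same-day strip narrows the gap without closing it.

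These are shares of conception days, not probabilities of pregnancy. The documents give neither the number of women of childbearing potential nor a conception rate. As an illustration on assumed inputs only (3 to 10 such women, 2% to 20% conceiving per year), the chance of at least one conception between screening and Visit 4 is 0.35% to 12%. A strip would find only part of these, as the table shows.

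**The case against.** The strongest reply is that the plan already handles this risk in proportion. It excludes pregnancy, tests for it at entry, requires double-barrier contraception, and asks about adverse events and medication before each session. Exposure is two 20-minute applications to the forehead from a device classed as non-significant risk, with no reported teratogenic association. Testing may have been meant purely as an entry check. All of this stands, and it is why the point is minor. It does not answer the narrow observation that nothing after screening looks for an unknown pregnancy.

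A second reply is that the percentages rest on a detection lag from outside the documents and do not measure benefit. That also stands. The ages of 7 and 21 days do not depend on the lag; the shares do.

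A reader might infer three stronger things that are not supported:

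- That retesting would mainly find pregnancies too early to detect at screening. Adding the two visits gives (7 + 14)/28 = 75% at L = 14, but this counts the 7 pre-screening days found at Visit 2 again at Visit 4, when a subject found positive would already have left. On distinct days the share is 67%, and at the shortest lag it is 48%, less than half.
- That the protocol contradicts itself. It does not: the exclusion, the single test and the session list are consistent with one another.
- That a subject found pregnant later could not be withdrawn, because the pregnancy item in 4.19.1 covers only the eligibility procedures. Item 5 of that list and the general right to end participation already allow withdrawal.

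**Conclusion.** The point holds as a minor safety improvement. Both active sessions proceed on a screening result nominally 7 and 21 days old (up to 14 and 28 after a shift), and no later procedure would reveal a pregnancy the subject does not know about. Under the assumed lag of 14 days (range 10 to 16), retests at Visits 2 and 4 would cover 21 distinct conception days that screening misses, of which 14 (67%, range 48 to 76%) fall before screening. The calendar figures assume sessions exactly one week apart. The absolute benefit is small and cannot be fixed from the documents. Neither the primary comparison of blood-flow changes nor any other analysis is affected.

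**What to change.** In 4.3.2 and 4.8.2, add a urine pregnancy strip for women of childbearing potential, run on the urine already collected for toxicology and read before light delivery. Visits 2 and 4 are where it can avert an active exposure. Include Visit 3 so that procedures stay identical for blinded subjects; it may also detect a pregnancy sooner. If the strip is positive, withhold light and withdraw the subject. Section 4.19.1 needs no change.

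The cost is a short amendment, at most 10 subjects x 3 visits = 30 strips, a few minutes per session and, rarely, a lost session. One practical point needs confirming. For the screening tests, 4.8.1 says "the tests will be processed by a laboratory at MGH", whereas for the sessions 4.8.2 says "The TLT sessions will occur once weekly for three weeks at the MGH Martinos Center for Biomedical Imaging in Charlestown". The documents do not say where session urine is read, so reading the strip at the session site is an assumption.

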4.3.3 Criteria for Enrollment – listed on pages 5-6

4.4 Subject Numbering

Subjects enrolled in the NIR-flow study will be identified by subject numbers 101 through 130 (to account for screen failures and drop-out before TLT sessions).

4.5 Sample Size

The NIR-flow study is expected to enroll 30 subjects, with 10 subjects who will be eligible and have analyzable data (at least 1 session post randomization).

4.6 Subject Confidentiality

Any information and data provided to Litecure Inc. or its designees in reference to any subject's participation in this investigation will be considered confidential. The Investigator will need to ensure that all subjects' anonymity will be maintained on all documentation submitted to Litecure Inc by completely redacting (eliminating or "blacking out") each subject's name and/or other identifying information. The identifying information will be replaced with the subject's study number and initials. The investigational site is not to provide to Litecure Inc information such as subject's telephone numbers, home address, personal identification numbers such as passport numbers, etc. Care must be taken by site research personnel when communicating with representatives from Litecure Inc in the form of telephone or electronic correspondence in not providing information that may disclose a subject's identity.

Documents associated with the study that are not intended to be submitted to Litecure Inc (e.g., signed Informed Consent Forms) must be kept in strict confidence by the Investigator. Only study site personnel, authorized Litecure Inc personnel, and regulatory authority inspectors will have access to these confidential files.

4.7 Study Visits

Study visits occur at MGH Center for Anxiety and Traumatic Stress Disorder (CATSD) in Boston.

The study involves screening, 3 TLT session paired with Diffuse Correlation Spectroscopy (DCS), and one follow-up visit.

Screening Visit (Week 1)

The screening visit is expected to take about 2 hours. The Principal Investigator (PI) at the site or a Sub-investigator will assess subjects against the inclusion and exclusion criteria. If a subject appears to qualify and agrees to participate in the study, then the subject will undergo the informed consent process prior to initiation of any study-specific activities. Screening Case Report Forms (CRFs) will be completed and subjects who qualify to participate in the study will proceed to the first Treatment Visit 1. If the subject does not meet entry criteria, the Investigator will document the subject's ineligibility for study participation and complete the appropriate CRFs.

TLT-DCS Visits – Visits 2-4 (Weeks 2-4)

There is one TLT session per week for 3 weeks. TLT-DCS Visit 2-4 will consist of all subjects receiving TLT, with DCS before and after TLT. Two groups of assessments will be conducted: **1. Before the TLT session** to reflect the symptoms endorsed in the past week: Anxiety Symptoms Questionnaire (ASQ), Symptoms of Depression Questionnaire SDQ, Quality of Life in Neurological Disorders (Neuro-QoL), Sexual Functioning Inventory (SFI), Systemic Assessment for Treatment Emergent Events (SAFTEE), and **2. After the TLT session** to reflect the immediate changes associated with the session: Positive and Negative Symptoms Questionnaire (PANAS), TLT Self-Report Questionnaire (TSRQ), Perceptions of Blinding Questionnaire (PBQ). Cognitive tasks will occur right after the TLT session. A detailed description of the study visits can be found below. EEG recording will immediately precede and follow the DCS-TLT-DCS triad and will in part overlap with the cognitive task.

Follow-Up Visit – Visit 5

All subjects will undergo assessments including ASQ, SDQ, Neuro-QoL, SFI, SAFTEE, PANAS and cognitive tasks at the follow-up visit (Week 5).

4.8 Detailed Study Visits

4.8.1 Screening Visit – Visits 1 (Week 1)

Purpose

The purpose of the Screening Visit will be to determine the eligibility of subjects for participation in the NIR-flow study.

Procedures

The screening visit will occur at the MGH Center for Anxiety and Traumatic Stress Disorders (CATSD) in Boston. At this visit subjects will be consented for the study, will receive a psychiatric evaluation, and will be screened for presence of psychiatric disorders using the Structured Clinical Interview for Diagnostic Statistical Manual-IV (SCID-IV). The SDQ, ASQ and PANAS will be used to assess for subthreshold symptoms. The SFI and NEURO-QoL will be used to assess sexual and cognitive functioning.

Routine laboratory tests (Urine Tox Screen and Urine Pregnancy Test) and complete physical exam including vitals and weight will be performed at screen; the tests will be processed by a laboratory at MGH.

Once all tests and procedures become available for review, the Investigator will then proceed to closely re-evaluate the subject for all the inclusion and exclusion criteria.

4.8.2 TLT-DCS Visits – Visits 2-4 (Weeks 2-4)

The TLT sessions will occur once weekly for three weeks at the MGH Martinos Center for Biomedical Imaging in Charlestown. Subjects missing one session will be allowed to still receive their TLT session, by shifting the overall study schedule of one week. The study PI will be an active participant in the delivery of the TLT. The PI and other collaborators from MGH CATSD will assist with the delivery of TLT. The device TPBM-1000 for the administration of the TLT will be provided by Litecure Inc. Litecure will provide training of MGH CATSD staff in the use of the device and will provide training certificates at the completion of the training.

The overall study visit is estimated to last about 1.5 hours. The TLT session is estimated to last about 50 min – 5 minutes of EEG before DCS, 10 minutes of DCS before TLT, 20 minutes of TLT, 10 minutes of DCS after TLT and 5 minutes of EEG after DCS. EEG recording will extend to cover at least part of the time devoted to the cognitive tasks. Study sessions will take place in an office dedicated to TLT treatment at MGH Martinos Center for Biomedical Imaging in Charlestown. Only the subject and the staff administering the TLT will be allowed in during the session. The subject will comfortably lie down on an exam bed or sit on a recliner. The sites of application of TLT (left and right forehead) will be inspected for any possible skin lesions (e.g. laceration or signs of inflammation) which would contraindicate the treatment. The study staff administering the TPBM device at the TLT-DCS sessions will appropriately remove any reflective objects to fall into or obstruct the path of the light energy produced by this device. Both the subject receiving the TLT and the study staff will wear protective eyewear in the form of goggles. During treatment sessions the office will be kept completely dark and a warning sign will hang at the office door. The staff will be provided training on basic safety procedures relative to the use of the device.

The trained staff administering the TLT will use utmost care to never shine the light in or near the eyes of the subject safety goggles will be selected based on the TLT biophysical properties, in accordance to the Occupational Safety and Health Administration (OSHA) guidelines. The delivery of the TLT is expected to last 20 min total (simultaneous application on the left and right forehead). The subject will be asked to rest for five minutes after the delivery of TLT. The skin at the sites of the application will be inspected again prior to dismissing the subject. A log with the dates of treatment delivery per each study subject will be kept at MGH CATSD (Boston).

During TLT-DCS Visit 2-4, subjects will receive TLT-c (Visit 2), TLT-s (Visit 3) and TLT-p (Visit 4).

The following tasks will be completed prior to every TLT session:

- Utox
- Concomitant medications form
- ADVERSE EVENTS FORM
- ASQ (self-rated)
- SDQ (self-rated)
- NEURO-QoL (self-rated)
- SFI (self-rated)
- SAFTEE (self-rated)
- PANAS (self-rated)
- EEG- Recording
- DCS – Spectroscopy

The following tasks will be completed after every TLT session:

- DCS – Spectroscopy
- EEG- Recording
- Cognitive tests
- PANAS (self-rated)
- TSRQ (self-rated)
- PBQ (self-rated)

Subjects shall be instructed to contact the investigator or a member of his staff at any time between visits concerning adverse events or worsening of symptoms.

